## 1. ABSTRACT

---

Muscle loss with age is considered to be an important cause of disability in older adults. However, current tools frequently used and recommended to measure muscle mass in trials have limitations: For example, DEXA (Dual-energy X-ray absorptiometry) and BIA (Bioelectrical impedance analysis)- both widely used in clinical trials cannot distinguish muscle tissue from non-muscle elements such as subcutaneous and intramuscular fat, skin, water and connective tissue

Deuterated creatine (D3Cr) dilution is a novel promising method that provides an accurate measure of the functional contractile tissue, without including the non-contractile elements, by measuring total body creatine. Our preliminary cross-sectional results in men aged >65 years show functional muscle mass (FMM) assessed by D3-Cr to be significantly associated with performance outcomes (SPPB, 400m walk, and chair stands) and long-term outcomes (incident mobility problems, serious injurious falls), while DEXA showed no associations. However, these are observational data and cannot determine a causative role of muscle per se on functional outcomes.

Hence, the objective of the pilot study is to assess the feasibility of our proposed future study to evaluate the role of muscle mass on functional outcomes. Specifically, the pilot study will randomize moderate to low-functioning older adults to a resistance training program or successful aging program to assess recruitment yields, participant adherence, retention, training program design aspects, sample size, and the cost of the main trial. Further, the impact of these changes in FMM on short-term performance outcomes, such as strength, walking speed, SPPB, self-reported measures, and balance will be examined.

## 2. BACKGROUND

---

It has now been well established that there is a progressive loss of muscle mass with aging. Prospective studies have shown this decline to be around 1% per year for both men and women. This dramatic change in anatomy with age has prompted the coining of the term *sarcopenia* (*sark*: flesh; *penia*: loss). Although not the sole cause of strength loss in older adults, the loss of muscle mass is thought to be a major cause of the decline in strength observed with age. Consequently, the loss of muscle and strength has direct adverse consequences on physical function leading to disability and mobility impairments. The recent establishment of ICD-10 code by CDC recognizing sarcopenia as an “independent reportable condition” further emphasize the role of muscle and muscle loss as major medical concern that needs immediate attention.

But, current tools frequently used and recommended to measure muscle mass in trials have limitations.

- DEXA and BIA- both widely used in clinical trials and recommended to diagnose sarcopenia, cannot distinguish muscle tissue from non-muscle elements such as subcutaneous and intramuscular fat, skin, water and connective tissue.
- Magnetic resonance imaging (MRI) and computed tomography (CT) can detect non-muscle tissue in body segments but are extremely expensive and cumbersome when the analysis involves total body skeletal muscle.

**Deuterated creatine ( $D_3Cr$ ) dilution** is a novel promising method that provides an accurate measure of the functional contractile tissue, without including the non-contractile elements, by measuring total body creatine. Briefly, the method involves ingestion of deuterated non-radioactive, labeled-creatine in a capsule and subsequently measuring total creatine from a single urine sample, without any special diet restrictions; thus making the method quite safe and feasible. Considering there is no gold standard *in vivo* measurement of total body skeletal muscle mass, construct validation studies have shown a strong correlation with MRI in both men and women (young and old) ( $r = 0.87$ ) and in animal studies ( $r = 0.95$ ). More importantly, our preliminary cross-sectional results in community-dwelling men aged  $>65$  years show functional muscle mass (FMM) assessed by  $D_3$ -Cr to be significantly associated with physical performance (SPPB, 400m walk, and chair stands) and long-term outcomes (incident mobility problems, serious injurious falls), while DEXA showed no associations.

However, these observational data cannot determine a causative role of muscle *per se* on functional outcomes. Additionally, there are no longitudinal or experimental studies that establish  $D_3$ -Cr as a standard measure of functional muscle mass (FMM). Our future study will use an experimental approach to evaluate the causative role and time course of FMM changes with  $D_3$ -Cr on functional outcomes. The accomplishment of this future longitudinal study will also validate this promising method for characterizing FMM in response to muscle-targeted interventions for low functioning older adults (e.g., selective androgen receptor modulators). A pilot study will fill necessary gaps that include feasibility and within-person variability of the  $D_3$ -Cr method that is currently unknown. Hence, the objective of the pilot study is to assess the feasibility of our proposed future trial.

Achieving the above aims will help in gathering feasibility information for our future study, but also provide novel insights into the time course of early FMM to resistance training and its relation to short-term outcomes. In addition, future studies can use  $D_3$ -Cr to evaluate the effectiveness of interventions to increase functional muscle mass.

### 3. SPECIFIC AIMS / OBJECTIVES

#### Primary objective

- To evaluate the feasibility of implementing the D3Cr method in a resistance training trial as it relates to participant adherence, retention, training program design aspects (intensity, volume, frequency & safety) sample size, and cost of the main study.

#### Secondary objectives

The secondary objectives are to:

- Evaluate and compare the time-course adaptations in skeletal muscle mass measured by D3-Cr and DEXA
- Correlate the **changes** in functional muscle mass with the change in walking speed, SPPB, strength, and balance.

### 4. RESEARCH PLAN

#### Trial Design

- The pilot study will be single-blind, parallel group, randomized controlled trial of **24 moderate to low functioning** participants randomized in a 1:1 allocation ratio to a high-intensity Resistance Training group (RT) or a Health Education comparator group (HE) for **14 weeks**. We chose the specified population since they are at a greater risk of disability and is often excluded from trials.

#### Schedule of Events

**Table 1. Study visit and schedule**

Schedule of Events	Training Intervention										
	Phone scr.	Scr. Visit	Baseline	Preparatory Phase	Training Phase	Week 1	Week 2	Week 8	Week 11	Week 14	Post-Test
Screening											
Basic eligibility phone screening	X										
Short consent		X									
Informed consent			X								
Physical exam, Medical History, Height		X									
Weight & Vitals			X					X			X
Interventions											
Resistance Training						↔	↔				
Successful Aging						↔	↔				
Assessments											
DEXA		X						X			X
D3Cr Dosing & Collection				X				X		X	
SPPB	X							X			X
Physical Functional Tests		X						X			X
Questionnaires	X							X			X

## **Participants**

24 low functioning, both males and females, with 12 participants in each of the treatment arm.

### **Inclusion criteria**

A participant must meet the following criteria to be eligible for inclusion in the study:

- men and women aged 70 or greater
- at high risk for mobility disability based on lower extremity functional limitations measured by Short Physical Performance battery (SPPB) with a score  $\leq$  8 out of 12
- could safely participate in the resistance training intervention as determined by medical history and physical examination.
- willing to give informed consent to be randomized to either the resistance training group or successful aging (Health Education) comparison group and willing to follow the study protocol

### **Exclusion criteria**

- Severe cardiac disease, including NYHA Class III or IV congestive heart failure, clinically significant aortic stenosis, history of cardiac arrest, use of a cardiac defibrillator, or uncontrolled angina
- Myocardial infarction, major heart surgery, stroke, deep vein thrombosis, or pulmonary embolus in the past 6 months
- Lung disease requiring either oral or injected steroids, or the use of supplemental oxygen
- Short, portable mental status questionnaire with 3 or more errors
- Severe arthritis (either osteoarthritis or rheumatoid arthritis) that severely limits mobility
- Severe lower back or shoulder pain that can worsen with weight lifting exercises.
- Cancer requiring treatment in the past 1 year (Melanomas excluded)
- Any present or recent history of severe psychiatric illness including depression that might preclude providing informed consent, safe participation, or compliance (self-report and investigator judgement)
- Development of chest pain or severe shortness of breath on the 400 m self-paced walk test
- Parkinson's disease or other serious neurological disorders; renal disease requiring dialysis; other illness of such severity that life expectancy is considered to be less than 12 months
- Current diagnosis of schizophrenia, other psychotic disorders, or bipolar disorder
- Current consumption of more than 14 alcoholic drinks per week
- Uncontrolled hypertension (systolic blood pressure  $>$  200 mm Hg and/or diastolic blood pressure  $>$  110 mm Hg)
- Currently on testosterone, Dehydroepiandrosterone (DHEA), or anabolic steroids.
- Undergoing physical therapy involving the lower extremities
- Currently enrolled in another randomized trial involving a pharmaceutical or lifestyle intervention. Observational studies are permitted
- Participation in progressive resistance exercise regimen ( $\geq$ 1 day/week) within the previous 6 months prior to screening.
- Weight change (intentional or not) over the last 6 months of  $>$  5% of body or plan to lose or gain weight during the study
- Any other cardiovascular, pulmonary, orthopedic, neurologic, or other conditions that in the opinion of the local clinician would preclude participation and successful completion of the protocol

### **Temporary Exclusion Criteria**

A person meeting any of the following temporary exclusion criteria at the time of screening will not be enrolled but may be re-screened later.

- Recent bacterial/viral infection (e.g. pneumonia) (< 2 weeks);
- Acute febrile illness in past 2 months;
- Severe hypertension, e.g., SBP > 200 mm Hg, DBP > 110 mm Hg
- Major surgery or fracture or hip/knee replacement (< 6 months);
- Hospitalization within the last 6 months ( Not ER visits)

**Premature Withdrawal from the Study:** A participant has the right to withdraw from the study at any time, for any reason, and without repercussion. The investigators have the right to withdraw a participant from the study in the event of an intercurrent illness, AE, treatment failure, protocol deviation, and for administrative, or other reasons. An excessive rate of withdrawals would render the study uninterpretable; therefore, unnecessary withdrawal of participants should be avoided.

**Sample Size:** Our goal is to enroll a total of 24 participants. Since studies looking at changes in functional muscle mass in response to resistance training are not available, the sample size was arrived based on budgetary constraints and minimum number of participants required to meet feasibility goals. Assuming a conservative 20% loss to follow up, we estimate 12 participants per group (10 evaluable participants after the 20% loss due to attrition) would inform variance of the outcomes and feasibility for powering a future large-scale RCT.

**Randomization:** Randomization will be executed via a computer algorithm using random block lengths and stratified by gender. To ensure concealment of the allocation, the randomization procedures will be performed by an investigator who are not involved in the assessments

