### **Adherence**

Adherence involves both attendance to scheduled sessions as well as the quality of the training that occurs during each session. Adherence to the exercise protocols are affected by personal, social and environmental factors. At a personal level, it is important to ensure that the goals of each participant are realistic. We recognize that social interactions between staff and participant as well as the broader social environment surrounding the study influence adherence. All staff will be instructed to engage with and be supportive toward all participants. We will also adopt a number of other strategies to improve attendance and quality of training sessions. Some strategies include, having trained interventionists to supervise training, including a preparatory phase to educate the participants about proper lifting technique, tailoring the training program based on the physical needs of the participant, maintaining a workout log to help motivation, monitoring missed visits so that the study coordinator can take prompt action and so forth

The physical environment and accessibility influence adherence. This includes such factors as ease of parking, transportation, and accommodations made for friends or significant others who may come to

training facilities to support participants via transportation, etc. At the time of baseline assessments, staff discuss these topics with each participant to be certain there are no significant barriers in this domain and/or to problem solve potential challenges that exist.

The comparator group will not participate in a resistance training intervention and hence pose a greater risk of dropping out. We expect, based on our previous experiences, that the flexibility exercises and health education classes offered every 2 weeks will serve an effective “active control” that will help to promote retention in the study. We will also provide an exercise prescription and education materials at the end of the study duration so that they can start a resistance training program outside the site.

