## Statistical plan

Data analysis will be conducted at the Biostatistics and Data Management Core under the direction of [name]. Our primary analysis will use an intention to treat approach in which participants are grouped according to randomization assignment without consideration of their adherence to the exercise or successful aging health education programs. We will also perform “per protocol” analyses to examine muscle adaptations in those individuals with adherence rates > 80%.

Although pilot studies are not powered for hypothesis testing, we will use a mixed effects model to assess changes in the outcomes with baseline measure serving as covariate. Associations between muscle mass and other outcomes will be explored using a correlational analysis

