## **Adverse events (AE) and serious adverse events (SAE)**

The study will collects and reports only Serious Adverse Events (SAEs) and (nonserious) AEs associated with the intervention or study procedures. Pre-existing conditions and preplanned procedures (surgeries or therapies) scheduled prior to signing the Informed Consent are not considered AEs/SAEs.

**Adverse events (AE):** For this study's purposes, an AE or experience is defined as any health-related unfavorable or unintended medical occurrence that happens after randomization. Examples of AEs include, but are not limited to, the following:

- A clinically significant laboratory or clinical test result at follow up assessments
- An event that requires a visit to a physician because it alters the participant's ability to exercise
- An event that occurs as a result of a study procedure which is not listed in the Risks section of the consent

**Serious adverse events (SAE):** SAEs are defined as events that may be harmful to the participant and/or may be serious enough to warrant either temporary or permanent discontinuation of the study intervention or study procedures,

either because they are intolerable or because they are judged to be potentially harmful. Consistent with NIH guidelines, SAEs are AEs that meet any of the following criteria:

- results in death
- is life-threatening
- requires inpatient hospitalization
- prolongs an existing hospitalization
- results in a persistent or significant disability/incapacity
- important medical events that investigators judge to represent significant hazards or harm to
  - participants, and may require medical or surgical intervention to prevent one of the other SAEs
  - listed in this definition (e.g., hospitalization, death, persistent disability)

**Relationship to study intervention:** The classification of potential relationship to the intervention is as follows.

- Not Related – AE is clearly not related to the intervention or procedure (e.g., temporal sequence of events is not consistent with administration of intervention or procedures, other causes are more plausible or causal relationship is implausible).
- Possibly Related – AE that follows reasonable sequence from administration of intervention or procedure but that could readily have been produced by several other factors.

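### Investigators may withdraw participants from the whole study, including for treatment failure or protocol deviation, and no visible text keeps those participants in outcome assessment

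*Combined protocol and SAP*

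**What the plan says.** The paragraph on premature withdrawal, placed under Temporary Exclusion Criteria, states: "The investigators have the right to withdraw a participant from the study in the event of an intercurrent illness, AE, treatment failure, protocol deviation". The sentence continues with administrative and other reasons. Treatment failure is not defined anywhere in the document. The paragraph closes with a caution: "An excessive rate of withdrawals would render the study uninterpretable; therefore, unnecessary withdrawal of participants should be avoided".

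Under Statistical plan, the primary analysis is by intention to treat: "participants are grouped according to randomization assignment without consideration of their adherence to the exercise or successful aging health education programs". Adherence has its own per-protocol analysis, planned "to examine muscle adaptations in those individuals with adherence rates > 80" percent. Changes in outcomes go into a mixed effects model with the baseline value as covariate. No rule for missing outcomes is given. The same section adds: "Associations between muscle mass and other outcomes will be explored using a correlational analysis". The matching secondary objective is to correlate changes "in functional muscle mass with the change in walking speed, SPPB, strength, and balance".

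The primary objective lists retention among the feasibility measures. The Retention section says payment for attending assessments does not depend on how much of the intervention a participant takes up. The definition of serious adverse events mentions stopping the intervention and stopping study procedures as separate possibilities.

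**The concern.** Stopping training and leaving the study are different events. An intention-to-treat analysis needs outcomes from people who stop training, respond poorly or deviate from the protocol. The withdrawal paragraph allows such people to be taken out of the study altogether, and nothing visible says they are measured afterwards.

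Two things are at stake. The first is the secondary analysis of muscle and function: withdrawal for treatment failure depends on response by its nature, and withdrawal for protocol deviation may depend on adherence, which the primary analysis is meant to disregard. The second is retention. The all-cause figure is the right one for sizing the next trial. Unless it is broken down, though, the pilot cannot show how much loss came from participants leaving and how much from a rule that the next trial could change.

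**Working it through.** **1. Does the withdrawal paragraph conflict with the analysis plan?**
- Grouping: a withdrawn participant can still be counted in the assigned arm, so the two passages do not contradict each other in wording.
- Data: the mixed model can use visits completed before withdrawal. A participant withdrawn before any follow-up visit has only a baseline value, which serves as a covariate, and so adds nothing to the analysis of change. Without a later value there is also no later change to enter the correlation.
- Mechanism: if withdrawal depends only on values already recorded and in the model, a likelihood-based mixed model can accommodate it. If it depends on an investigator's judgement of response or adherence that is not in the model, it may not. The documents do not say which would apply.

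**2. Does other text supply the follow-up?**
- The caution against unnecessary withdrawal limits how often the right is used. It does not say what happens to those withdrawn.
- The payment rule implies that poorly adherent participants who remain in the study are still measured. It does not reach someone formally withdrawn.
- The definition of serious adverse events distinguishes intervention from procedures, but it is a definition and not a follow-up rule.

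**3. The plan's own loss figure.** Inputs from Sample Size: 24 participants, 12 per arm, 20% loss, 10 evaluable per arm.
- 12 × (1 − 0.20) = 9.6, which rounds to the stated 10.
- Implied losses: 12 − 10 = 2 per arm, or 2 × 2 = 4 in all.
- Implied retention: 20/24 = 10/12 = 83.3%. Exact (Clopper-Pearson) 95% intervals are 62.6% to 95.3% for 20/24 and 51.6% to 97.9% for 10/12.

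**4. Scale of one investigator withdrawal.**
- Retention: 1/24 = 4.2 points overall; 1/12 = 8.3 points in the arm.
- Share of the loss allowance: 1 of 2 in that arm, or half.
- Illustration with an assumed count: two investigator withdrawals on top of the four losses give 18/24 = 75.0% (53.3% to 90.2%). That is a 25% loss against the planned 20%, with no further participant having chosen to leave.

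**5. Scale in outcome data.** Table 1 is damaged in extraction and its week labels cannot be relied on. Each outcome row carries three marks. Taking the first as the screening or baseline measure leaves two follow-up points (an assumption).
- Planned follow-up values per outcome: 24 × 2 = 48 overall; 12 × 2 = 24 per arm.
- Withdrawn before the first follow-up: 2/48 = 4.2% of values, or 2/24 = 8.3% of the arm's.
- Withdrawn between the two: 1/48 = 2.1% of values, and 1/12 = 8.3% of the arm's final values.

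These figures apply to any lost participant, whatever the reason. They give scale and do not measure bias.

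**The case against.** The strongest reply is that the right is discretionary, requires no withdrawal and comes with an explicit caution. Harm needs three things: the right is used, assessment then stops, and the loss is related to outcome. The documents show none of them happening. The payment rule and the wording on serious adverse events suggest that the authors expected some people to reduce or stop training while still being assessed. The pilot is not powered for hypothesis testing, and the intervals above are far wider than the effect of one withdrawal. All of this stands, and it is why the point is minor.

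Three stronger readings are tempting and are not supported.
- A reader might infer that the withdrawal rule contradicts intention to treat. It does not: grouping by assigned arm is unaffected, and the difficulty is missing later data.
- A reader might infer that losses will differ by arm. The Adherence section does say "The comparator group will not participate in a resistance training intervention and hence pose a greater risk of dropping out", but it goes on to expect the classes to support retention. One example of an adverse event is "An event that requires a visit to a physician because it alters the participant's ability to exercise", but that is an example of an event and not a trigger for withdrawal. In the other direction, the section on expected adverse events says that soreness, joint pain and similar complaints do not require stopping the intervention. The note to Table 2 also lets training values vary with ability and availability, so many departures are permitted tailoring. No arm difference is shown.
- A reader might infer that follow-up after withdrawal is provided for nowhere. Consent pages were removed before review, so only the visible text can be judged.

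**Conclusion.** The point holds in a limited form. As written, the protocol permits withdrawal from the study on grounds tied to response or adherence, and no visible text continues outcome assessment. If the right is used and assessment stops, the analysis loses the outcomes that an adherence-blind comparison is meant to include, and retention mixes investigator decisions with participant choices. The size and direction of any bias cannot be derived, because no withdrawal rate or reason pattern is given. Each such withdrawal would cost 8.3 points of an arm's retention and half of that arm's planned loss allowance, which is small against the pilot's imprecision. The conclusion rests on two assumptions: that withdrawal from the study means no further assessment, and that the removed consent pages do not say otherwise. Priority is minor.

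**What to change.** Amend the premature-withdrawal paragraph to separate stopping the intervention from ending follow-up, so that treatment failure, protocol deviation or non-adherence does not by itself end outcome assessment. Participants who stop the intervention stay in the intention-to-treat set and are invited to the remaining scheduled assessments, with their consent and where the investigator judges assessment safe. The investigator's authority to stop the intervention or study procedures for clinical reasons is left unchanged. Report all-cause retention, with investigator-initiated withdrawals, participant withdrawals and loss to follow-up shown separately by arm.

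The cost is one wording change, one table and a few assessments at visits already scheduled. If all 4 losses implied by the plan were investigator-initiated before the first follow-up, the upper limit is 4 × 2 = 8 extra assessment points per outcome, on the two-follow-up reading of Table 1. Some of these may be incomplete where a test is judged unsafe.
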